## Management of treatment groups:

Participants will be randomized into one of three treatment arms – BiPAP, CPAP, conventional therapy. In addition to standard therapy, the three treatments will consist of:

- BiPAP group (Trilogy device) to be started in the ER after randomization, pressures 16/5 cm H2O, with rate of 10 to 15 / minute plus hourly salbutamol.
- CPAP group (Trilogy device) to be started in ER after randomization. Starting pressure 8 cm H2O, increased to 10 cm H2O if no clinical response and hourly salbutamol.
- Conventional therapy, hourly nebulized salbutamol, nebulized ipratropium q 6 hrly, magnesium sulphate 50 mg/kg IV (4 doses q 6 hrly), loading dose of aminophylline 6 mg/kg IV if no progress.

#### General care for all three groups:

All three treatment arms will receive the following standard care:

- Oxygen to keep saturations  $\geq$  92% for all three groups.
- Standard course of oral steroid: dexamethasone 0.3mg/kg/dose once daily for 4 consecutive days,
- On-call research coordinator to assess the patients and record data.
- If a patient in any of the treatment groups deteriorates, they will be managed in the usual way with medical review and admission to ICU as required.

#### Criteria for study termination:

- Failure to tolerate BiPAP (persistent agitation and tachycardia, refusal to wear mask) resulting in the need for its discontinuation despite appropriate administration of sedation.
- Signs of impending respiratory failure in either study arm should immediately prompt discussion with the ICU team and discontinuation of study participation

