## **Research Methods:**

## Overview of study design:

The aim of the study is to determine if the use of NIV, for children admitted to hospital with an acute exacerbation of asthma, reduces their work of breathing, need for adjunctive medication, length of hospital stay, and need for intubation and mechanical ventilation. Study design will be prospective, randomized and controlled. The tightly fitting face mask necessary for NIV makes it impossible to make this a blinded study.

The principal enrollment criteria will be children over 2 years of age presenting to the ER with acute asthma. After diagnosis, all children are treated with standard therapy (systemic steroids plus 3 doses of inhaled salbutamol and 1 dose of inhaled ipratropium over a 1 hour period then hourly salbutamol). The principal decision between discharge track and admission track will be made at 2 hours after first steroid dose. Admission criteria are based on sequential PRAM scores.

After initial asthma treatment and observation in the emergency room, to determine which patients can be discharged home, those who need admission will be asked to join the study, then consented and randomized. There will be three treatment groups:

- BiPAP: standard steroid dose, hourly salbutamol and BiPAP at 15/5 cm H2O by face mask with rate 10 to 15/min, oxygen as needed.
- CPAP: standard steroid dose, hourly salbutamol and 8 to 10 cm H2O constant pressure by face mask, oxygen as needed.
- Conventional therapy: standard steroid dose plus hourly nebulized salbutamol, nebulized ipratropium q 6 hrly, magnesium sulphate 50 mg/kg IV (4 doses q 6 hrly), loading dose of aminophylline 6 mg/kg IV if no progress, oxygen as needed.

All children will be admitted to a small 3 bed respiratory unit. They will be closely monitored and objectively scored every 4 hours using the PRAM asthma clinical severity score (Pediatric Respiratory Assessment Measure)[18]. End points will be: time to reach room air, time to reach PRAM score <3, numbers requiring intubation and mechanical ventilation and medication use. Those children older than 5 or 6 yrs, will also perform lung function tests twice daily. Projected patient enrollment will be at least 30 in each arm. Estimated study duration is 6 months.

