## Safety Monitoring:

Although there are decades of experience confirming the safety of NIV in children, this study represents a significant change to well-established conventional therapy so extra levels of observation of the treatment groups have been included in the study design:

- The study hospital has agreed to set aside a 3 bed ward dedicated to the duration of the study. It will be staffed by 4 nurses and 2 qualified pediatricians who will provide continuous 24 hr a day coverage for the study participants. Staff salaries for the study will be covered by study funds.
- Since this is an open study, we plan to perform an interim review of adverse events after 10 patients have been enrolled in each treatment arm. The clinical reviewer will be [name] and the statistical reviewer will be [name] both from Children's Hospital, Vancouver.
- The head of ER at PGIMER, Chandigarh, has agreed to be the local external monitor. The research coordinators will be the most likely people to pick up adverse events. All RCs will be trained in the study protocol, including the reporting process in the event of an adverse event. Nursing staff are also aware of the need for extra monitoring and the need to report potential problems.

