## Sample size calculation.

In order to have an impact on common practice, we would define a significant treatment effect as a 25% reduction in time to PRAM of 3. In order to demonstrate this effect with a power of 80% and a 5% chance of a type 1 error, we need an estimate of mean time to PRAM of 3 plus standard deviation from previous published work. Unfortunately, there is very little published information to act as a guide. The only published pediatric study that provides relevant data is a pilot study by Basnet et al.[17] Using only 10 patients in each arm, they showed BiPAP reduced time in ICU (48+/- 16 hrs vs. 36+/-14 hrs). They used a clinical score to guide management but it was different to the PRAM. If we take the higher of these standard deviations as a rough guide to the average ICU admission time and combine it with a power of 80% and type 1 error risk of 5%, we will need 26 patients in each arm to detect a 25% reduction in time to PRAM of 3. It must be emphasized that the shortage of relevant literature makes this only a rough estimate.

Statistical analysis.

Outcomes in the two treatment arms of the study (BiPAP and CPAP), will be compared to those in the control group (conventional acute paediatric asthma treatment). The principal end points will be analysed in the following ways:

1. Changes in asthma score over time.

The PRAM respiratory distres score is based on objective and subjective observations so the final values are non-parametric. Multiple comparisons over time, between treatment group and control, will be made with the Kruskal-Wallace test with Dunn's posthoc test.

2. Time to reach asthma score <3.

The value will be measured in hours after starting treatment so the values will be parametric. Comparison between treatment and control values will be made using t test. 3. Total number of pharmacological treatments per day.

The total number of drug treatments will be calculated for each 12 hour period. These are parametric values. Comparisons between control and treated group of repeat measures over time, will be made by analysis of variance with Tukey's post-hoc test. 4. Lung function tests.

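### Mask intolerance is listed as a reason to end study participation, with no rule keeping these children in follow-up or in their randomised arm

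*Combined protocol and SAP*

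**What the plan says.** The section Criteria for study termination has two entries. The first is "Failure to tolerate BiPAP (persistent agitation and tachycardia, refusal to wear mask) resulting in the need for its discontinuation despite appropriate administration of sedation". The second is "Signs of impending respiratory failure in either study arm should immediately prompt discussion with the ICU team and discontinuation of study participation". CPAP intolerance is not mentioned, although CPAP is also given by face mask.

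The trial is open, because "The tightly fitting face mask necessary for NIV makes it impossible to make this a blinded study" (Overview of study design). The control regimen, under Management of treatment groups, involves no mask: "Conventional therapy, hourly nebulized salbutamol, nebulized ipratropium q 6 hrly, magnesium sulphate 50 mg/kg IV", with aminophylline if there is no progress.

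On data collection, children are to be "objectively scored every 4 hours using the PRAM asthma clinical severity score" (Overview of study design). General care for all three groups provides for an "On-call research coordinator to assess the patients and record data". Safety Monitoring describes a dedicated unit with staff "who will provide continuous 24 hr a day coverage for the study participants".

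On analysis, the statistical text that follows the sample size calculation says: "Outcomes in the two treatment arms of the study (BiPAP and CPAP), will be compared to those in the control group". It excludes nobody. It also names no analysis population and no rule for a child who stops before reaching the PRAM target. Measured Outcomes counts treatment failures transferred to ICU but has no count of mask intolerance.

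**The concern.** The first entry, read alone, says only that the device stops. But it stands under a heading about study termination, and the entry beside it ends the child's participation. A coordinator following the page would have good reason to take the child out of the study.

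Applied that way, the rule removes children after randomisation, for an event that can happen only in a mask arm, on the judgement of staff who know the arm. Agitation, tachycardia and mask refusal despite sedation could plausibly go with age or severity, and so with recovery time. The BiPAP–control comparison would then set mask-tolerant children against all controls, including those who would not have tolerated a mask. The same applies to CPAP if staff extend the rule to it. Randomisation does not protect that comparison, and enrolling more children does not repair it.

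**Working it through.** **1. What the text settles.** Four provisions could keep an intolerant child in the data:

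- *Four-hourly PRAM scoring and the recording coordinator* apply to children in the study. Neither is said to continue after the mask is stopped.
- *Round-the-clock cover* is for study participants. Whether a child who meets a termination criterion still counts as one is not stated.
- *The outcome for treatment failure* is tied to ICU transfer. A child who refuses the mask and stays on the ward is not counted there.
- *The planned comparison* names the arms but does not say that every child is analysed in the arm assigned.

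None closes the gap. A child who in practice stays under observation would still contribute to the listed outcomes; only a separate count of intolerance would then be missing.

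**2. Inputs.** From the sample size section: control mean 48 h, SD 16 h (the higher of the two quoted), target reduction 25%, so 0.25 × 48 = 12 h; alpha 5%, taken as two-sided. From the Overview: 30 per arm. Assumed, because the documents are silent: the proportion intolerant, *p*, and the recovery gap, *g* (intolerant minus tolerant, in hours).

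**3. The plan's own figure.** The plan states 26 per arm. The normal approximation gives n = 2 × 16² × (1.96 + 0.84)² / 12², which rounds up to 28; the exact t test gives 29. That is close to the plan's self-described rough estimate, and nothing below depends on the difference.

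**4. Bias if every intolerant child is left out of BiPAP.** With no true effect, both arms have the same overall mean. The tolerant children's mean lies below it by *p* × *g*, so this is the bias in favour of BiPAP.

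**5. False-positive rate.** SE = 16 × √(1/n + 1/30), where n is the number left in the BiPAP arm. The noncentrality is bias / SE, and rejection is from the noncentral t at two-sided 5%.

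| p | g | n | Bias | Share of 12 h | SE | Rejects for BiPAP | Rejects against | Total |
|---|---|---|---|---|---|---|---|---|
| 10% | +12 h | 27 | 1.2 h | 10% | 4.24 h | 4.6% | 1.3% | 5.9% |
| 20% | +16 h | 24 | 3.2 h | 27% | 4.38 h | 10.7% | 0.4% | 11.1% |
| 20% | 0 | 24 | 0 | 0% | 4.38 h | 2.5% | 2.5% | 5.0% |
| 20% | −12 h | 24 | −2.4 h | −20% | 4.38 h | 0.6% | 7.7% | 8.4% |

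Removing one subgroup also narrows the spread. With the overall SD held at 16 h, the SD among tolerant children is √(256 − p(1 − p)g²): 15.6, 14.7 and 15.3 h in the three non-zero rows. Simulation with those values (400,000 trials each) gives 5.8%, 11.2% and 8.4%. With all 30 children analysed as randomised it gives 5.0%, 5.0% and 5.1%.

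**6. Power from lost numbers alone** (true effect 12 h, SD 16 h): 81.5% at 30 v 30, 79.3% at 27 v 30, 76.7% at 24 v 30. The loss is modest; the main issue is bias.

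**The case against.** The strongest reply is that the plan never says these children are excluded. The first entry speaks of stopping BiPAP, and the statistical text drops nobody, so the harm needs two unstated steps: follow-up ends, and the child leaves the analysis. The neighbouring entry can also be turned round. Children with impending respiratory failure are those whom the plan intends to count as ICU transfers or intubations, so meeting a termination criterion cannot wholly mean leaving the dataset. The children are inpatients in a small dedicated unit, and nothing moves them out when the mask comes off. The criterion names observable signs and requires failure despite sedation, which is narrower than free discretion.

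Much of this stands. Exclusion is a reasonable reading, not a stated rule, and complete data are possible. But the argument from ICU counts covers children who deteriorate. It gives no time to the PRAM target for a child who refuses the mask, stays on the ward and is no longer treated as a participant. That child is the one at issue.

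It is also fair that the magnitudes are assumptions: the milder adverse case moves the error rate only from 5.0% to 5.9%, and 11.1% needs one child in five intolerant after sedation with a gap of a full SD. The silence on CPAP is probably a drafting slip and adds little.

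**Conclusion.** The concern holds as a gap in the plan, not as a demonstrated bias. The termination rule, followed in its most natural reading, takes children out of one side of the comparison after randomisation, and no other text retains them.

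Over the cases shown, the bias runs from 2.4 h against BiPAP to 3.2 h in its favour, against a 12 h target, and the false-positive rate from 5.0% to 11.1%. These figures rest on assumed intolerance rates and recovery gaps, SD 16 h, and exclusion of every intolerant child. If such children recover no differently, there is no bias and only a small loss of power. Confidence is medium because the wording is ambiguous. It should be corrected before enrolment, since times that were never recorded cannot be recovered after discharge.

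**What to change.** Four changes of wording:

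1. In Criteria for study termination, state that intolerance in either mask arm (BiPAP or CPAP) stops the mask but not study participation.
2. State that PRAM scoring and data recording continue on the planned schedule until the endpoint.
3. In the statistical analysis text, state that every child is analysed in the arm to which they were randomised.
4. In Measured Outcomes, add the number in each arm whose mask was discontinued for intolerance.

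The scoring, recording and staffing are already planned, so the operational cost is small. The statistical cost is that mask-arm results will include children who came off the mask. If 10% do so and gain nothing, the expected effect is 12 × 0.9 = 10.8 h and power at 30 per arm is 72.9%; at 20% it is 12 × 0.8 = 9.6 h and 62.8%. Against the 79.3% and 76.7% available when those children are dropped and there is no recovery gap, that is 6.4 and 13.9 points lower. Keeping 80% power in those cases would need more children. The diluted effect is nonetheless the effect of offering the mask to children admitted with acute asthma, which exclusion would conceal.

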#### Exclusion criteria:

- Clinical suspicion of bacterial pneumonia: focal crackles or bronchial breathing, and/or major chest x-ray findings.
- Impending respiratory failure at presentation requiring direct PICU admission
- Any contraindication to BiPAP use including altered mental status, recent bowel surgery, intractable vomiting, inability to protect airway, pneumothorax.
- Receiving maintenance dose of oral steroid at time of hospital admission
- History of serious unrelated illness such as congenital heart disease or bronchopulmonary dysplasia.

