#### Measured Outcomes:

- Length of time to reach a PRAM score of  $\leq 3$
- Time to room air.
- Total medication use per 12 hr period.
- Numbers failing treatment and transferred to ICU.
- Numbers in each group requiring hospital readmission within 48 hours of discharge
- Time to reach FEV1 >80% predicted in those children able to perform PFTs.

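### Failing children leave the study, and no rule keeps them in the time-to-PRAM comparison that sized the trial

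*Combined protocol and SAP*

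**What the plan says.** Two events are listed under *Criteria for study termination*. One is "Failure to tolerate BiPAP (persistent agitation and tachycardia, refusal to wear mask) resulting in the need for its discontinuation despite appropriate administration of sedation". The other is: "Signs of impending respiratory failure in either study arm should immediately prompt discussion with the ICU team and discontinuation of study participation". The second is explicit that participation ends.

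*Sample size calculation* ties the trial to one outcome: "we would define a significant treatment effect as a 25% reduction in time to PRAM of 3". *Statistical analysis*, item 2, says of that outcome: "Comparison between treatment and control values will be made using t test".

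On where scores are taken, *Overview of study design* has all children "admitted to a small 3 bed respiratory unit. They will be closely monitored and objectively scored every 4 hours using the PRAM" score.

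Some follow-up beyond exit is implied. *Measured Outcomes* includes "Numbers failing treatment and transferred to ICU" and "Numbers in each group requiring hospital readmission within 48 hours of discharge". The overview makes intubation with mechanical ventilation an end point. *General care for all three groups* has a coordinator on call who assesses children and records data. None of these promises a PRAM score after a child leaves the unit or the study.

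**The concern.** A t test on hours needs a number for every randomised child. The children this exit rule removes are those doing worst, whose recovery times are likely to be long. If their scoring stops, their times are unknown and the analyst must choose: leave them out, or give them some late value. The plan does not choose, and the trial is open-label, so the choice could be made with results in view.

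Leaving out slow recoverers makes an arm look faster than it was. If one arm loses more of them, the difference between arms moves for reasons unrelated to treatment. Unequal exit is possible: the intolerance criterion names BiPAP only, and ICU referral is decided by staff who know the arm. A time that was never scored may not be recoverable later.

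**Working it through.** **Inputs from the protocol.** Control mean 48 h and higher SD 16 h (*Sample size calculation*; these are ICU stays from a 20-patient pilot that used a different score). Target: a 25% reduction, 0.25 × 48 = 12 h. Power 80%, type I error 5% (two-sided assumed). Enrolment at least 30 per arm (*Overview of study design*). No exit rate is given.

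**The plan's own figure.** n per arm = 2(1.96 + 0.84)² × (16/12)² = 2 × 7.85 × 1.78 ≈ 28. The plan states 26, so it is reproduced to within two children; an exact t calculation gives 29 with SD 16 and 26 with SD 15. With 30 per arm and every time observed, power for 12 h is about 81%.

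**Hand check of the bias.** If a fraction p leaves and leavers average D hours slower than their arm, deleting them lowers the arm mean by D × p/(1 − p). Take D = 16 h (one SD, assumed):

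- 10% versus 5%: (0.111 − 0.053) × 16 ≈ 0.9 h.
- 20% versus 10%: (0.250 − 0.111) × 16 ≈ 2.2 h. This slightly overstates the shift, because at higher exit rates the leavers are less extreme.

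**Simulation, no true effect, leavers deleted.** 30 per arm, Normal times, t test. The chance of leaving follows logit p = a + k(T − 48)/16, with k = 1 or 2 and a set to give the stated average loss. Where runs differed, the range is shown.

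| Loss, BiPAP / control | Shift, BiPAP − control | Two-sided error |
|---|---|---|
| 10% / 5%, k = 1 | about −0.7 h | 5.1–5.5% |
| 10% / 5%, k = 2 | about −1.0 h | 5.7–5.8% |
| 20% / 10%, k = 1 | about −1.3 h | 5.8–6.0% |
| 20% / 10%, k = 2 | −1.9 h | 7.4–7.9% |
| 5% / 10%, k = 1 and 2 | +0.7 and +1.0 h | as for 10% / 5% |
| 10% / 10% or 20% / 20% | 0 h | about 5% |
| 5% severity-linked in both arms, plus 5% random in BiPAP only | −0.01 and +0.04 h | about 5% |

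The last row matters. An excess of mask intolerance that is unrelated to recovery does no harm to the comparison beyond smaller numbers.

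**True 12 h benefit, one common exit rule, leavers deleted** (k = 1, then 2).

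| Control loss | Mean observed benefit | Power | Power, same numbers lost at random |
|---|---|---|---|
| 5% | 11.6, 11.2 h | 79%, 77% | 80%, 80% |
| 10% | 11.3, 10.6 h | 76%, 73% | 78%, 78% |
| 20% | 10.9, 9.7 h | 70%, 65% | 74%, 74% |

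Here deletion is conservative, and part of the power loss is only smaller n.

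**Does the choice of rule matter?** For the same 10% / 5% leavers under no effect, deletion gives −0.7 to −1.0 h, assigning 72 h gives +0.3 to +0.6 h, and following the children to their true time gives 0 h. Two defensible rules differ in sign, though both shifts are small.

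**Scale.** If true times are nearer 24 h with SD 8 h (an assumption), the deletion shift halves to 0.3–0.5 h, while assigning 72 h gives about +2 h. Any window must therefore be set from expected recovery times.

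**The case against.** The strongest reply is that this is silence, not a stated error. The termination section does not say leavers are dropped from analysis, all children are to be scored in the unit, a coordinator records data, and several outcomes need information after ICU transfer. Exits are also limited: *Exclusion criteria* removes "Impending respiratory failure at presentation requiring direct PICU admission" and children with BiPAP contraindications, and sedation is tried before the mask is abandoned. All of this is true. It narrows the point without closing it, because none of it secures a PRAM time after participation ends.

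Four stronger readings are tempting and are not supported:

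- **That the plan excludes failures from analysis.** It does not say so; it leaves the matter open.
- **That the bias will favour BiPAP.** The respiratory-failure trigger is not arm-specific as written, and the documents do not link mask intolerance to recovery time. Nothing shows which arm would lose more slow recoverers.
- **That false positives nearly double.** Counting only results that favour BiPAP, 10% versus 5% loss gives 3.5–4.4% against 2.5%. The opposite tail shrinks, so two-sided error stays below 6%.
- **That exit time could stand in for recovery time.** This would shift the result by −2.3 to −2.6 h if exits fall evenly over 4–24 h. But item 2 defines the value as time to reach the score, which a child who left unrecovered has not done.

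Nor is the t test itself at fault here: it is adequate if every time is observed.

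**Conclusion.** The point stands as a gap that should be closed, at modest size. It is certain that participation ends for failing children and that no rule covers post-exit PRAM scoring, the analysis set or non-recovery. How much harm follows is conditional. With 10% versus 5% loss linked to slow recovery, the shift is about 0.7–1.0 h against a 12 h target, with two-sided error at most about 6%. With 20% versus 10% it is about 1.3–2.0 h and 6–8%. The sign follows whichever arm loses more slow recoverers. With no true effect, bias vanishes if severity-linked exit is equal across arms or if the excess exit is unrelated to recovery. With a real benefit and a common exit rule, deletion mildly shrinks the effect and lowers power.

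These figures rest on assumed exit rates, Normal times, and ICU hours borrowed from a pilot, which the protocol itself treats as rough. Enrolling 30 rather than 26 restores some precision but does not cure selection.

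**What to change.** 1. Reword *Criteria for study termination* so that both events stop study treatment only. The clinical triggers stay as they are. Continue 4-hourly PRAM scoring, including in ICU, until the threshold is reached or the child is discharged.
2. State in *Statistical analysis* that all randomised children are analysed in their assigned arm. A child moved to ICU or taken off the mask counts as not recovered until the threshold is actually reached. Pre-specify one rule for those who never reach it: for example worst rank with a rank test, or a pre-set window chosen from expected recovery times. The t test may stay if every time is observed.

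The cost is some wording and a few extra PRAM scores. If leavers' times are obtained, the comparison is unbiased and power stays near 81%. The real downside arises if non-recovery is frequent and unrelated to the course of illness. With an illustrative 72 h window, 1, 2 or 3 such children of 30 in each arm reduce power to about 75%, 68% or 63%; 3 of 30 in BiPAP alone reduces it to about 44%.

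### The termination criteria end study participation, not only treatment, at impending respiratory failure, so most intubations and the sickest children's 48-hour readmission status could go unrecorded

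*Combined protocol and SAP*

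**What the plan says.** Overview of study design includes in the aim reductions in "length of hospital stay, and need for intubation and mechanical ventilation", and its end points include "numbers requiring intubation and mechanical ventilation and medication use". Measured Outcomes adds "Numbers failing treatment and transferred to ICU" and "Numbers in each group requiring hospital readmission within 48 hours of discharge".

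Criteria for study termination has two bullets. The first is failure to tolerate BiPAP, despite sedation, to the point where BiPAP has to be stopped. The second reads: "Signs of impending respiratory failure in either study arm should immediately prompt discussion with the ICU team and discontinuation of study participation".

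Four other places bear on this:

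- Exclusion criteria removes children with "Impending respiratory failure at presentation requiring direct PICU admission".
- Overview of study design gives CPAP as "constant pressure by face mask, oxygen as needed", so there are two mask arms. Management of treatment groups uses the same device for both.
- General care for all three groups provides for "On-call research coordinator to assess the patients and record data". It sends a child who deteriorates to medical review, and to the ICU if required, without mentioning an exit from the study.
- Statistical analysis compares each mask arm with conventional therapy. It gives no method for intubation, ICU transfer or readmission, and no rule for children who leave early.

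**The concern.** The second termination bullet does not separate stopping the allocated treatment from leaving the study. Its trigger, impending respiratory failure, is the state that normally comes just before intubation. A coordinator who follows the bullet ends a child's participation at the moment the most serious end point becomes likely, and before the readmission window opens.

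At stake is whether the counts of the most serious outcomes are complete and comparable across arms. In an open-label trial, leaving continued recording to individual judgement also lets follow-up differ by arm. The efficacy tests under Statistical analysis are a separate matter.

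The first bullet raises a smaller question. It sits under a heading about study termination and names one of the two mask treatments. If it too means leaving the study, the BiPAP arm has an exit that neither CPAP nor conventional therapy has.

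**Working it through.** The plan gives no figure for intubation, ICU transfer or readmission, so there is none to reproduce. Its 26 per arm concerns time to a PRAM score of 3 and is not in question here. The check is mainly one of sequence; the arithmetic only illustrates scale.

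**Sequence**

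1. Children in impending failure who need direct PICU admission at presentation are excluded, so an enrolled child reaches that state later.
2. A child who is then intubated will usually have shown signs of impending failure first, which triggers the exit.
3. The ICU transfer coincides with the trigger and can be counted. Intubation comes after it, and readmission within 48 hours of discharge later still.
4. General care for all three groups provides an ICU route that does not mention leaving the study. The supportable statement is therefore that *most* intubations would be lost, not all.

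**Intubation** (risk p assumed; planned enrolment at least 30 per arm, so N = 90)

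Missed events are at most N × p, reached if every intubation follows the exit. The probability of at least one true event is 1 − (1 − p)^90.

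| p | Per arm (30p) | Among 90 (90p) | P(at least one) |
|---|---|---|---|
| 3% | 0.9 | 2.7 | 93.6% |
| 5% | 1.5 | 4.5 | 99.0% |
| 10% | 3.0 | 9.0 | 99.99% |

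**BiPAP-only intolerance bullet** (illustration, and only if it means leaving the study)

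Let q be the share who are mask-intolerant, r their ICU risk, and 10% the ICU risk in the others. All three are assumed.

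- True risk in a mask arm = q·r + (1 − q)·10%. With q = 20% and r = 30%: 6% + 8% = 14%, or 4.2 of 30.
- BiPAP as recorded = (1 − q)·10% = 8% of all randomised, or 10% of those who stay. Transfers lost = 30 × 0.20 × 0.30 = 1.8.
- Shift in the BiPAP risk = −q·r = −6 points (all randomised), or −q·(r − 10%) = −4 points (stayers only). Over q of 10–30% and r of 20–40% it runs from −2 to −12, or from −1 to −9.
- If the conventional arm is fully counted, the same shift enters BiPAP versus conventional, which is the comparison the plan makes.

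**Readmission status lost** (same inputs, and taking every ICU transfer as an exit, which overstates the loss if some children follow the general-care route)

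- BiPAP: q + (1 − q)·10% = 20% + 8% = 28%, or 8.4 of 30; range 19–37%.
- CPAP: q·r + (1 − q)·10% = 14%, or 4.2 of 30; range 11–19%.

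**Precision with complete follow-up**

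For 3/30 in each of two arms, the Wilson 95% limits are 3.5% and 25.6%. The Newcombe half-width is √[(10 − 3.5)² + (25.6 − 10)²] ≈ 16.9 points, so the interval is 0 ± 16.9 points.

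**The case against.** The strongest reply is that the sponsor plainly wants these events, since it lists them as outcomes. If participation is read as study treatment, the termination section agrees with the outcome lists. No section says that data collection stops. Coordinators record data in all arms. Safety Monitoring adds 24-hour cover, training in adverse-event reporting and an interim adverse-event review, so an intubation would probably be noticed. The documents said to be attached in section 9 are not visible and might settle the matter.

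This stands as an argument about intent, and it makes the harm conditional. It does not change the instruction. Neither the general-care section nor Safety Monitoring says that recording continues once participation has ended, and noticing an event is not the same as counting it by allocated arm.

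The reply is stronger on the intolerance bullet. That bullet speaks only of stopping BiPAP; the words about ending participation are in the other bullet, and leaving the study rests on the heading alone. A child who cannot tolerate BiPAP could also be counted as a treatment failure. A reader might infer that the plan builds in a known advantage for BiPAP over CPAP on ICU transfer. The documents do not support that: the exit is an inference from the heading, the stated comparisons are with conventional therapy, and every risk in the illustration is assumed.

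It is also fair that these three outcomes have no planned test, and that correct counts would still be imprecise.

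**Conclusion.** The concern holds in a conditional form. The plan instructs staff to end study participation at signs of impending respiratory failure, and nothing visible says outcomes are still collected. If that is followed as written, most intubations and the 48-hour readmission status of the sickest children are lost. The ICU transfer at that exit is not.

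A reader might go further and infer that the intubation count must come out at zero, or that the sponsor planned to stop collecting data. Neither follows: the general-care section offers another route to the ICU, and the sponsor may have intended to keep counting.

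The size depends on risks the plan does not give. At assumed intubation risks of 3–10%, at most about 3 to 9 events among 90 children are at stake. The unequal handling of BiPAP and CPAP intolerance is a secondary point. It could distort comparisons with control as well as between the masks, but its size cannot be estimated from the documents. Mentioning either arm in a three-arm trial is probably loose wording and needs only tidying.

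**What to change.** In Criteria for study termination:

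- Retitle the section *Criteria for stopping the allocated treatment*.
- In the second bullet, replace the words that end participation with: *discontinuation of the allocated treatment; data collection continues for all randomised children until 48 h after hospital discharge*.
- Replace the reference to either arm with *any of the three arms*.
- Word the intolerance bullet as failure to tolerate *the BiPAP or CPAP mask*, as a reason to stop the mask only.

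In Statistical analysis, add one three-row table of intubation, ICU transfer and 48-hour readmission by allocated arm, with all randomised children as denominator. Give risk differences for BiPAP versus conventional and CPAP versus conventional with 95% intervals, and describe them as imprecise.

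The cost is small. Coordinators follow a few children into the ICU, the 48-hour contact is already needed for the readmission outcome, and consent may need one line on data collection after treatment stops. The sample size and the existing tests do not change. The intervals stay wide; the gain is counts that are complete and comparable between arms.
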